### **Exclusion criteria**

Patient should not have any of the following to be included:

1-history of hypersensitivity or infusion related reactions after administration of monoclonal antibodies.

2-prior use of standard antiviral therapy (remedsvir or favipravir).

3-Current use of controversial antiviral therapy (hydroxychloroquine, ivermectin, nitazoxanide, oseltemavir, acyclovir, ribavirine, lopinavir/rotavirus, sofosbuvir, dectasevir, semipiravir, azithromycin).

4-patients expected to die within 48 hours.

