## **Sample Size:**

A total sample sizes of 246 patients would achieve at least 80 % power to detect a risk difference of 0.2 (20%) in the 28-day all-cause mortality (primary outcome) with a significance level ( $\alpha$ ) of 0.05 and 95% confidence level using the ANOVA or Kruskal-Wallis test of independent proportion in G\*Power software. To compensate for the estimated loss-to-follow-up and increase the study power, we will increase the sample size in both remdesivir and favipravir groups to be 106 patients compared to 53 patients in Antibodies cocktail Group As Antibodies cocktail product is available for only about 50 COVID-19 patients. In addition, the ratio (1:2:2) is the closest to reality according to number of patients who receive each drug.

The mortality data was estimated from the average mortality in August, September, and October 2021 at the Mansoura University Isolation Hospital among all hospitalized patients. Mortality rate is found to be about 360 cases in these 3 months (120 cases / month). The online system has been used to obtain mortality rate in these three months.

The current admission rate at the Mansoura University – Isolation Hospital is 250 cases per month on average; our needed sample is about 250 cases.

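### At least 80% power is claimed for a 20-point mortality difference, but no 28-day risk is stated for any arm; the only mortality input is a monthly count of deaths

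*Combined protocol and SAP*

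**What the plan says.** All the planning figures are in the Sample Size section of the combined protocol and SAP.

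- **Power claim:** "A total sample sizes of 246 patients would achieve at least 80 % power to detect a risk difference of 0.2 (20" percent) in 28-day all-cause mortality, at α = 0.05, attributed to ANOVA or Kruskal-Wallis in G*Power.
- **Source of the mortality data:** "The mortality data was estimated from the average mortality in August, September, and October 2021 at the Mansoura University Isolation Hospital among all hospitalized patients".
- **The figure itself:** "Mortality rate is found to be about 360 cases in these 3 months (120 cases / month").
- **Admissions:** "The current admission rate at the Mansoura University – Isolation Hospital is 250 cases per month on average". This stands in a separate paragraph, beside the number of patients needed.
- **Arms:** 53 on the cocktail and 106 on each comparator, a total of 265. Cocktail supply is limited to about 50 patients.

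Inclusion criteria require PCR-confirmed moderate, severe or critical disease. Exclusion criterion 4 removes "patients expected to die within 48 hours". No section gives an assumed 28-day risk for the cocktail, remdesivir or favipiravir.

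**The concern.** The powered outcome is a proportion: deaths by day 28 among enrolled patients. The planning figure is deaths per calendar month. It differs from what is needed in four ways.

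- It has no denominator for August to October 2021. The 250 per month is described as current.
- It covers every inpatient, not only those eligible.
- It includes patients whom the 48-hour exclusion would remove.
- It is not limited to 28 days.

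The net direction of the mismatch is unknown: the 48-hour exclusion lowers the eligible risk, while leaving out any mild cases would raise it.

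This matters because the variance of a proportion depends on its level. A fixed 20-point difference is easier to detect at low risk than near 50%, and it is a very different relative effect at 30% than at 60%. Without arm risks, a reader can neither verify the 80% nor judge whether the target effect is plausible.

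**Working it through.** **Inputs from the Sample Size section:** N = 246; effect 0.2; α = 0.05; power at least 0.80; three groups; final arms 53/106/106; 120 deaths per month; 250 admissions per month. **Assumptions:** one arm (cocktail) 20 points lower and the two comparators equal; pairwise tests two-sided at 0.05; no dropout.

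**1. Reproducing 246 without a mortality rate.** For the one-way ANOVA F test the noncentrality is λ = N·f². With f = 0.2 and three groups, N = 244 is the smallest total that reaches 80% (power 0.800). Rounded up to equal groups this is 3 × 82 = 246, with λ = 246 × 0.04 = 9.84 and power 0.804.

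**2. A second route to 246.** For two proportions, 40% versus 20%:

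n = [1.96√(2 × 0.30 × 0.70) + 0.842√(0.40 × 0.60 + 0.20 × 0.80)]² / 0.20² = 81.2, so 82 per arm, and 82 × 3 = 246.

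The documents state neither 40% nor 20%. The two routes agree because, in equal groups, a 20-point drop from 40% is exactly f = 0.200. At 30%, 48% and 60% the same drop is f = 0.223, 0.191 and 0.189.

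**3. The only crude risk the figures yield.** 360/3 = 120 per month, and 120/250 = 48%. The plan does not make this division. It pairs deaths from August to October with a current admission rate.

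**4. Power for a true 20-point difference.** For the three-group test, λ = Σnᵢ(pᵢ − p̄)² / [p̄(1 − p̄)] on 2 degrees of freedom. For 0/1 data the Kruskal-Wallis statistic is (N − 1)/N times the Pearson chi-square, so this also represents the planned test.

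- Equal arms, 48% vs 28%: p̄ = 0.4133; λ = 2.187/0.2425 = 9.02; power 0.77.
- 53/106/106, 40% vs 20%: p̄ = 0.36; λ = (53 × 0.16² + 212 × 0.04²)/0.2304 = 1.696/0.2304 = 7.36; power 0.68.
- 53/106/106, 48% vs 28%: p̄ = 0.44; λ = 1.696/0.2464 = 6.88; power 0.65.

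| Comparator risk (assumed) | Cocktail risk | Relative reduction | 246 equal, 3-group | 53/106/106, 3-group | 53 vs 106, pairwise |
|---|---|---|---|---|---|
| 30% | 10% | 67% | 0.89 | 0.76 | 0.84 |
| 40% | 20% | 50% | 0.81 | 0.68 | 0.73 |
| 48% | 28% | 42% | 0.77 | 0.65 | 0.68 |
| 60% | 40% | 33% | 0.76 | 0.65 | 0.67 |

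The relative reduction is 20 points divided by the comparator risk. Going from 246 in equal arms to 265 at 1:2:2 lowers power in every row, because the cocktail arm falls from 82 to 53.

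**The case against.** Four counter-arguments deserve weight.

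- **The count may never have entered the calculation.** A reader might infer that the sample size rests on an invalid base rate. The documents do not support that: 246 follows from f = 0.2 alone. The 40% versus 20% route means a base rate cannot be ruled out either. This stands, and it moves the problem to the meaning of 0.2 and the unstated arm risks.
- **The plan never claims 48%.** A reader might infer that it uses an inflated 48% risk, or that there is no denominator at all. Neither is right. A denominator is printed, but it is unmatched and serves recruitment. The 48% is used here only as the one risk that the printed figures yield.
- **A lower eligible risk helps power.** This stands. Within the range tabulated, if the 48-hour exclusion lowers the risk, power for a fixed 20 points rises: from 0.65 at 48% to 0.76 at 30% on the three-group test. What becomes harder is the implied relative reduction, from 42% to 67%.
- **A null result would still be interpretable.** A reader might infer that it could not be read against the target. It could: a confidence interval for the risk difference can be compared with 20 points whatever the planning rate was.

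None of this supplies the missing risks or shows that the stated power holds at the planned allocation.

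**Conclusion.** The concern holds in this limited form: the plan claims 80% power for an absolute difference whose power depends on a base rate it never states, and the mortality figure offered in support is a count that is not a 28-day risk in eligible patients.

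With 246 in equal arms the claim is met at 40% versus 20% (about 0.81) and missed at 48% versus 28% (about 0.77). At the planned 53/106/106 it is met at neither: about 0.68 and 0.65 on the three-group test, 0.73 and 0.68 for the cocktail against one comparator. Over comparator risks of 30% to 60% the three-group power at that allocation stays below 80%. The pairwise comparison passes 80% only near the lower end.

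These figures rest on assumed comparator risks, equal comparator arms and no loss to follow-up. They use the 1:2:2 split in the Interventions section, Table 2 and the Sample Size section. The Population section says 2:1:1, and the two must be reconciled. That the 0.2 is really Cohen's f is a likely explanation, not an established one.

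**What to change.** Rewrite the Sample Size section as follows.

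1. From the same online system, report deaths within 28 days divided by admissions, both for August to October 2021. Restrict them, as far as records allow, to PCR-confirmed moderate, severe or critical patients who survived 48 hours. That is the nearest record-based match to exclusion criterion 4, which is a prospective judgement.
2. State the assumed 28-day risk in each of the three arms and the relative reduction implied.
3. State whether 0.2 is a risk difference or Cohen's f.
4. Restate power at 53/106/106 for the planned test, over a short range of comparator risks.

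The cost is one query and a rewritten paragraph. No extra patients are required to report power correctly. Restoring 80% is another matter: at 48% versus 28% and 1:2:2 it would take 375 patients, so 375/5 = 75 on the cocktail, beyond the stated supply of about 50. The downside is that the stated power will probably be below 80%, and the 20-point target may look more ambitious once its relative size is shown.

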## **Ethical approval:**

Ethical approval will be taken from the Research Ethics Committees of Mansoura and Tanta University. Informed consents will be obtained from all participants in this research. Privacy of participants and confidentiality of data will be maintained. Benefits of the intervention to the patients outweigh expected risks. Any unexpected risk appeared during the course of the research will be cleared to participants and the ethical committee on time. All study procedures will obey the standard of the Declaration of Helsinki (1964) principles.

## **Data Quality and Safety:**

We will collect the data directly into an electronic CRF , no papers are used to collect clinical data to avoid transmission of infection from area of isolation.  
Patient confidentiality will be kept before, during and after the study

## **Publishment of Study results and funding:**

We would register protocol and results in Clinicaltrial.gov and aim to publish this study in peer-review journals.

Funding:

The company of intervention drugs will not support with additional fund or interests.  
The investigators declare no relevant conflict of interest

Conflict of interest:

none

